10.3 Analyses Plans	
10.4 Accrual estimates	
11. RFFFRENCES:	19

PROTOCOL SYNOPSIS

TITLE	A Pilot Study of ⁶⁸ Ga-PSMA-11 PET/MRI and ⁶⁸ Ga-RM2
	PET/MRI for Biopsy Guidance in Patients with Suspected
	Prostate Cancer
STUDY PHASE	Phase 2 pilot study
INDICATION	Prostate cancer
INVESTIGATIONAL	⁶⁸ Ga-PSMA-11; also known as:
PRODUCTS	• DFKZ-11
	HBED-CC PSMA
	The "Heidelberg compound"
	⁶⁸ Ga-RM2; also known as:
	Bombesin
	• BAY86-7548
SAMPLE SIZE	20 participants
PRIMARY OBJECTIVE	To evaluate ⁶⁸ Ga-PSMA-11 PET/MRI and ⁶⁸ Ga-RM2 PET/MRI
	for biopsy guidance in patients with suspected prostate cancer.
EXPLORATORY	• Correlation of ⁶⁸ Ga-PSMA-11 uptake and Gleason score at
ENDPOINTS	biopsy
	 Correlation of ⁶⁸Ga-RM2 and Gleason score at biopsy

SCHEMA

LIST OF ABBREVIATIONS AND DEFINITION OF TERMS

Ga-68; ⁶⁸ Ga	Gallium-68
IRB	Institutional Review Board
IV	Intravenous
MRI	Magnetic resonance imaging
NPV	Negative predictive value
PPV	Positive predictive value
PET	Positron emission tomography
SUV	Standardized Uptake Value
PSMA	Prostate-specific membrane antigen
GRPR	Gastrin releasing peptide receptor
PRCA	Prostate cancer

1. OBJECTIVE

Specific Aim

To evaluate ⁶⁸Ga-PSMA-11 PET/MRI and ⁶⁸Ga-RM2 PET/MRI for biopsy guidance in patients with suspected prostate cancer.

2. BACKGROUND

2.1 Preliminary information

Prostate cancer (PRCA) kills ~29,000 American men each year (1). However, most of the ~180,000 new cases diagnosed each year are not deadly. While the 50% drop in PRCA specific mortality in the US occurred concurrently with systematic PSA screening starting in the 1980s, the PLCO randomized trial of PSA screening showed no survival benefit, and ERSPC in Europe showed a small but positive benefit to PSA screening (2, 3). Two significant limitations of PSA testing contribute to the poor results of these trials and form the basis of this proposal:

The 1st limitation is that PSA has poor sensitivity and specificity with ~15% of men with PRCA having a normal PSA (4) while 60-80% of men who are biopsied are found to have no cancer, either because there is none and the PSA test was falsely positive or the cancer is missed by the biopsy (5). Until recently, transrectal ultrasound (TRUS) has been the only widely available used imaging modality. Because of the major limitations of TRUS for PRCA detection, diagnosis is most commonly accomplished by systematically sampling the entire prostate using 12 needles passed through the rectum under TRUS guidance, rather than directing biopsy to any particular target seen in the gland on TRUS images. This biopsy procedure can be painful and is associated with significant and increasing rates of infectious complications (6, 7). Since autopsy studies show that many men have small, indolent cancers that are not likely to be life threatening (8), PSA driven biopsy leads to overdiagnosis of indolent cancers (9) that are not clinically significant. The ideal approach would be to eliminate unnecessary biopsies in men with no cancer or indolent cancer, and selectively biopsy men with aggressive cancers who are more likely to benefit from therapy.

The 2nd limitation is that PSA screening and biopsies miss a significant number of aggressive cancers, either by under-sampling high grade cancers, or by underestimating of tumor volume (10-12). The ideal approach would be to direct biopsies towards the areas of most aggressive tumor, so that biopsy accurately reflects the severity of their disease.

In response to these shortcomings of PSA screening as well as the significant treatment associated side effects (13), the management of localized PRCA has changed dramatically in the past 5 years to directly address the problem of over-treatment (5). One of the greatest changes has been the increased use of Active Surveillance (AS) in men with low grade, low risk PRCA (14). In the US, rates of AS have increased from 5-9% in 1990-2010 to 40%, while in Europe, rates are 80 to 90% (15-17). Gleason scoring is an established marker of outcome and is the most important factor used in selecting patients for AS (5). Low grade cancers (Grade group 1 or Gleason score 3 + 3 + 6) are recommended for AS, while cases > 3 + 4 (or in some cases > 4 + 3) are recommend for definitive therapy (18). Therefore, accurate identification of cases with grade > 3 + 4 is critical for determining initial treatment vs AS. Second, ancillary tests, such as the urinary test PCA3 (a IncRNA over-expressed in PRCA), as well as the

IRB-48151 Page 7 of 22 CONFIDENTIAL Protocol version 2; 15 November 2021

Prostate Health Index and 4Kscore have emerged (both assessing molecular forms of PSA) (19-21). These tests have been calibrated to identify men who do not need biopsy, and can decrease biopsy rates by 10-20%. However, many unnecessary biopsies continue to occur, and none of these tests effectively identifies aggressive PRCA. For example, neither the PCA3 or 4K score provide clinically meaningful prediction of outcomes in men on AS and cannot be used in clinical decision-making in this large and growing cohort of men (22, 23). New technologies are critically needed to eliminate unnecessary biopsies in men with no cancer or indolent cancer, and to better identify men with aggressive forms (≥ 3 + 4) of PRCA.

Recently, novel PET tracers that target PRCA cells have emerged as promising methods to improve PRCA imaging. PET tracers such as ¹⁸F- or ¹¹C-labeled choline and ¹¹C-acetate are used at selected institutions in the USA (24, 25) but uptake in benign prostatic hyperplasia (BPH) or inflammatory lymph nodes (26, 27) limits their clinical utility. A new synthetic amino acid ¹⁸F-FACBC suffers from limited specificity as its uptake in PRCA is reported to be similar to that in BPH (28). Prostate-specific membrane antigen (PSMA) is a cell surface protein significantly over-expressed in PRCA cells, and anti-PSMA antibodies labeled with ⁶⁸Ga and ¹⁸F-labeled radiotracers can detect PRCA relapses and metastases by binding to the extracellular domain of PSMA. While PSMA appears to be a very promising molecular imaging target (29, 30), it does not detect all recurrences (31, 32) and is not specific to PRCA only (33, 34). False positives have also been reported (35-37). Gastrin releasing peptide receptor (GRPR) has emerged as a novel imaging target which is also highly expressed in PRCA and has much lower expression in benign prostate tissue including BPH and inflammation (38). This high specificity provides an advantage over current choline- and acetate-based radiotracers. GRPR can be targeted by its natural ligand GRP or other bombesin-like peptides. Compared to antibodies, peptides are usually cleared faster, penetrate tissue more rapidly, show lower antigenicity, and can be synthesized in large quantities relatively easily, making GRPR an attractive target (39). Also, a clear difference of RM2 expression level between Gleason patterns 3 and ≥ 4 has been shown with higher expression of RM2 antigen significantly associated with primary Gleason pattern ≥ 4, high Gleason score (≥ 8), larger tumor volume, and advanced tumor stage (40). Furthermore, 5-year PSA failure-free survival was significantly lower in the higher expression groups (40).

The sponsor-investigator [name] holds Investigational New Drug applications (INDs) for both ⁶⁸Ga-RM2 and ⁶⁸Ga-PSMA-11 (IND and IND and the group has significant experience using both tracers in currently ongoing clinical studies at our institution. To improve the performance of MRI imaging in the prostate, one possible solution could be to combine molecular imaging strategies. MRI provides excellent soft tissue contrast and mpMRI has significantly improved PRCA detection in the prostate. PET/MRI can increase the specificity of MRI alone when using PRCA specific PET tracers (41). We propose testing this multimodal imaging platform in patients with early stage PRCA to understand its performance characteristics for detection, particularly for aggressive disease (defined as high grade > 3 + 4).

2.2 Clinicaltrials.gov

This protocol will be registered on Clinicaltrials.Gov. ClinicalTrials.gov outcomes are described in Section 2.4.3.

IRB-48151 Page 8 of 22 CONFIDENTIAL Protocol version 2; 15 November 2021

2.4 Study Design

This is a pilot study with a total of 20 participants with suspected prostate cancer. All patients will first be seen by a Stanford Cancer Institute physician and then referred if appropriate on clinical grounds to [name] or his colleagues for this study. Eligible participants will undergo baseline assessments at enrollment. The following steps will take place after the participant has signed the written consent (participants will be randomized to have ⁶⁸Ga-RM2 first followed by ⁶⁸Ga-PSMA11 within 2 weeks or ⁶⁸Ga-PSMA11 first followed by ⁶⁸Ga-RM2 within 2 weeks [50/50 chance for each schedule]).

- 1. Participants will be given a copy of the consent form s/he signed.
- 2. Participant will be asked to drink 1 to 2 glasses of water before arrival at the clinic
- 3. Vital signs (heart rate, blood pressure) will be recorded
- 4. Participant will be injected IV with 140 \pm 20% mBg of ⁶⁸Ga-RM2
- 5. Participant will void immediately prior to the scan
- 6. Approximately 45 minutes after the radiopharmaceutical IV administration, data acquisition will begin in the pelvic region and move toward the head. First, localizer MRI scans will be performed to define the table positions. After correct positioning of the spatial acquisition windows is ensured, the combined PET/MRI acquisition will be initiated with 3 to 5 table positions at a 2 to 4 minute acquisition time per table position.
- 7. Vital signs (heart rate, blood pressure) will be recorded again at the completion of the study, and the participant will be dismissed.

IRB-48151 Page 10 of 22 CONFIDENTIAL Protocol version 2; 15 November 2021

8. Participants will be contacted at 24 to 72 hours following the scan in order to collect any adverse events.

The same will be repeated for ⁶⁸Ga-PSMA11 (within 2 weeks of ⁶⁸Ga-RM2):

- 1. Participant will be asked to drink 1 to 2 glasses of water before arrival at the clinic
- 2. Vital signs (heart rate, blood pressure) will be recorded
- 3. Participant will be injected IV with 3 to 7 mCi of 68Ga-PSMA11
- 4. Participant will void immediately prior to the scan
- 5. Approximately 45 to 60 minutes after the radiopharmaceutical IV administration, data acquisition will begin in the pelvic region and move toward the head. First, localizer MRI scans will be performed to define the table positions. After correct positioning of the spatial acquisition windows is ensured, the combined PET/MRI acquisition will be initiated with 3 to 5 table positions at a 2 to 4 minute acquisition time per table position. Only MR sequences required for attenuation correction of PET data will be acquired.
- 6. Vital signs (heart rate, blood pressure) will be recorded again at the completion of the study.
- 7. Participants will be contacted at 24 to 72 hours following the scan in order to collect any adverse events.

2.4.1 Objectives of the Study

Primary

• To evaluate ⁶⁸Ga-PSMA-11 PET/MRI and ⁶⁸Ga-RM2 PET/MRI for biopsy guidance in patients with suspected prostate cancer.

Exploratory

- Correlation of ⁶⁸Ga-PSMA-11 uptake and Gleason score at biopsy
- Correlation of ⁶⁸Ga-RM2 and Gleason score at biopsy

2.4.2 Endpoints

Primary Endpoints

Number of participants with successful PET-based biopsy guidance

Exploratory Endpoints

- Observation of SUV_{max} from ⁶⁸Ga-PSMA-11 uptake and Gleason score at biopsy
- Observation of SUV_{max} from ⁶⁸Ga-RM2 uptake and Gleason score at biopsy

2.4.3 ClinicalTrials.gov Outcomes

Primary Outcome

Title: Successful PET-based Biopsy Guidance

Description: Number of participants with biopsy results correlated with imaging findings (ie, prostate uptake on ⁶⁸Ga-PSMA-11 and ⁶⁸Ga-RM2 scans)

The outcome will be reported as the number of participants without dispersion for which PET-based biopsy guidance is successfully obtained.

Timeframe:

Safety outcome: No

IRB-48151 Page 11 of 22 CONFIDENTIAL Protocol version 2; 15 November 2021

Secondary Outcome

None.

3. PARTICIPANT SELECTION AND ENROLLMENT PROCEDURES

3.1 Inclusion Criteria

- ≥ 18 years-old
- Suspected prostate cancer
- Planned prostate biopsy
- Able to provide written consent
- Karnofsky performance status of ≥ 50 (or ECOG/WHO equivalent)

3.2 Exclusion Criteria

- Patients not capable of getting PET study due to weight, claustrophobia, or inability to lay still for the duration of the exam
- Metallic implants (contraindicated for MRI)

3.3 Informed Consent Process

All participants will be provided a consent form describing the study with sufficient information for participants to make an informed decision regarding their participation. Participants must sign the IRB-approved informed consent prior to participation in any study specific procedure. The participant must receive a copy of the signed and dated consent document. The original signed copy of the consent document must be retained in the medical record or research file.

3.4 Study Timeline

3.4.1 Primary Completion:

The study will reach primary completion 24 months from the time the study opens to accrual.

3.4.2. Study Completion:

The study will reach study completion 36 months from the time the study opens to accrual.

4. IMAGING AGENT INFORMATION

4.1 Study Agents

This protocol will utilize ⁶⁸Ga-RM2 and ⁶⁸Ga-PSMA11 as radioimaging agents.

4.1.1 68 Ga-RM2

The PET radiopharmaceutical ⁶⁸Ga-RM2 has previously been identified as ⁶⁸Ga-DOTA Bombesin or BAY86-7548. This is not an FDA-approved product, and is described within IND to which this protocol is submitted. The structure of ⁶⁸Ga-RM2 is represented in Figure 3.

IRB-48151 Page 12 of 22 CONFIDENTIAL Protocol version 2; 15 November 2021

BAY 86-7548

Figure 3: Chemical structure of ⁶⁸Ga-RM2

The administered dosage of 68 Ga-RM2 will be 140 mBq \pm 20%, administered IV. Measured human dosimetry data are available from published data (47). 68 Ga-RM2 is rapidly excreted through the kidneys to the urinary bladder and accumulated predominantly in the pancreas and liver. Maximum peak uptake of the total injected radioactivity was seen in the urinary bladder contents and the liver, with approximately 36% and 14%, respectively.

The organ with the highest absorbed dose was the urinary bladder wall at 0.61 mSv/MBq, followed by the pancreas at 0.51 mSv/MBq. The mean effective dose (14) was 0.051 mSv/MBq. Thus, the effective dose from a 140-MBq injected radioactivity is 7.7 mSv, which could be reduced to roughly 4.76 mSv with frequent bladder voiding (1-hr voids). To summarize the results of the published human dosimetry study, there were no observed adverse events to the radiopharmaceutical. The measured dosimetry showed that the critical organ with ⁶⁸Ga-RM2 is the urinary bladder, followed by the pancreas. The effective dose of ⁶⁸Ga-RM2 reported (0.051 mSv/MBq) is approximately twice as much as those of ⁶⁸Ga-DOTA-TOC (0.023 mSv/MBq), ⁶⁸Ga-DOTA-NOC (0.025 mSv/MBq), ⁶⁸Ga-DOTA-TATE (0.021 mSv/MBq) and ⁶⁸Ga-NOTA-RGD (0.022 mSv/MBq) (43-46).

4.1.2 68 Ga-PSMA11

The PET radiopharmaceutical ⁶⁸Ga-PSMA11 will also be utilized, and has previously been identified as DFKZ-11; HBED-CC PSMA; or the "Heidelberg compound." This is not an FDA-approved product, and is described within IND which is cross-referenced to IND The structure of ⁶⁸Ga-PSMA11 is represented in Figure 4.

[figure not shown]

Figure 4: Chemical structure of ⁶⁸Ga-PSMA11.

IRB-48151 Page 13 of 22 CONFIDENTIAL Protocol version 2; 15 November 2021

The administered dosage of ⁶⁸Ga-PSMA-11 will be 111 to 259 mBq (3 to 7 mCi), administed IV. There are 2 publications on dosimetry for ⁶⁸Ga-PSMA-11 (PMID: 27260521; 28012435). The first lists 0.0236 mSv/MBq for the mean effective dose, while the other indicates 0.0258 mSv/MBq. We used the maximum potential administered activity of 7 mCi and the higher of the reported dosimetry values. Therefore, 259 mBq x 0.0258 mSv/MBq + 6.68 mSv.

To summarize the results of the published human studies, there were no observed adverse events to the radiopharmaceutical. The measured dosimetry showed that the critical organ with ⁶⁸Ga-PSMA-11 is the spleen, followed by the stomach wall; pancreas; and bladder wall. The effective dose of ⁶⁸Ga-PSMA-11 reported (0.0258 mSv/MBq) is similar to those of ⁶⁸Ga-DOTA-TOC (0.023 mSv/MBq), ⁶⁸Ga-DOTA-NOC (0.025 mSv/MBq), ⁶⁸Ga-DOTA-TATE (0.021 mSv/MBq) and ⁶⁸Ga-NOTA-RGD (0.022 mSv/MBq) (43-46).

4.2 Source of the Study Agent

Molecular Imaging Program at Stanford (MIPS) Satellite Radiochemistry Facility [name]

4.3 Ordering

Ordered in Radiology Information System (RIS), address per above.

4.4 Agent Accountability

The RIS is password-protected and part of the electronic medical records.

5. IMAGING SPECIFICS

5.1 Modality or Modalities to be used PET/MRI

5.2 Details of Imaging (ie, dynamic, static, number of scans, etc)

A localizer MRI scan will be performed at 45 minutes after injection of 140 mBq of ⁶⁸Ga-RM2 (or 3 to 7 mCi of ⁶⁸Ga-PSMA11, depending on randomization) to define the table positions. After correct positioning of the spatial acquisition windows is ensured, the combined PET/MRI acquisition will be initiated with 3 to 5 table positions at a 2 to 4 minute acquisition time per table position. A volumetric T1 acquisition with fat-water separation and motion correction to enable free-breathing will be obtained at each table position and used for the generation of attenuation maps and for anatomic allocation of the PET results. Simultaneously with the start of the T1 MRI sequence, the PET acquisition will start at the same table position, thus ensuring optimal temporal and regional correspondence between MRI and PET data. The PET acquisition time will be 4 minutes per table position, taking delayed acquisition times and radioactive decay into account. As the T1 will take less than 4 minutes, a rapid diffusion weighted MRI will also be performed. After completion of the PET acquisition, the table will be moved to the next table position and the procedure will be repeated. Upon completion of the

IRB-48151 Page 14 of 22 CONFIDENTIAL Protocol version 2; 15 November 2021

PET acquisition for all stations, volumetric post-contrast T1- and T2-weighted MR images may be obtained at multiple stations as needed.

A localizer MRI scan will be performed at 45 minutes after injection of 3-7 mCi of ⁶⁸Ga-PSMA11 (or ⁶⁸Ga-RM2, depending on randomization) to define the table positions. After correct positioning of the spatial acquisition windows is ensured, the combined PET/MRI acquisition will be initiated with 3 to 5 table positions at a 2 to 4 minute acquisition time per table position. Only MR sequences required for attenuation correction of PET data will be acquired. Participants will be randomized to have ⁶⁸Ga-RM2 first followed by ⁶⁸Ga-PSMA11 within 2 weeks or ⁶⁸Ga-PSMA11 first followed by ⁶⁸Ga-RM2 within 2 weeks (50/50 chance for each schedule).

5.3 Image interpretation

The PET/MRI scans will be interpreted by ABNM certified Nuclear Medicine physicians and an ABR-certified radiologists. Drs [name], [name], [name], and [name] have significant clinical experience and will be blinded to the participants' medical history and the results of other imaging modalities. Consensus read will be obtained for each scan. Each lesion will be tabulated and a comparison of lesion detection by each tracer will be conducted.

The study team will communicate the results of the scans to the referring (treating) physicians. Additional imaging/biopsy may be performed as a result of the research scan data.

PET and MRI data will be imported in the biopsy device to assist with lesion localization during the biopsy procedure.

6. STUDY PROCEDURES

6.1 Pre-Study

Potential subjects will be referred by treating physicians for participation in this imaging study. The following procedures will occur pre-study:

- · Review of eligibility criteria
- Obtain informed consent
- Collect demographics
- Review medical history, including any concomitant medication.

6.2 Imaging Days

Subjects will undergo 2 separate clinic visits for imaging. On each imaging day, subjects will receive an intravenous (IV) injection of investigational imaging agent (⁶⁸Ga-RM2 or ⁶⁸Ga-PMSA11) and undergo PET/MRI image collection as described above.

6.3 Follow-up

Active subject participation ends after the 24 to 72 hour post-scan Safety Follow-up. Investigators will follow subjects by chart review for 12 months post-scan to record any standard of care biopsies or imaging results. The investigators will assist with identification of lesions that can be biopsied, based on ⁶⁸Ga-RM2 and/or ⁶⁸Ga-PMSA11 PET/MRI findings.

IRB-48151 Page 15 of 22 CONFIDENTIAL Protocol version 2; 15 November 2021

If a subject transfers clinical care outside of Stanford Healthcare during the chart review clinical follow-up period, investigators will request permission to contact the treating physician.

6.4 Criteria for Removal from Study

The Protocol Director may withdraw subjects from the study for one or more of the following reasons: failure to follow the instructions of the Protocol Director and/or study staff; determination that continuing the participation could be harmful to the subject; the study is cancelled or other administrative reasons.

6.5 Alternatives

The alternative is to not participate in the study.

7. STUDY CALENDAR

			24 to 72 Hours	
	Pre-Study	Scan Date	Post-Scan	12 Months
Informed consent	Х			
Demographics	Х			
Medical history	Х			
⁶⁸ Ga-RM2		X a		
⁶⁸ Ga-PSMA11 (within 2 weeks)		X a		
Follow-up Call to Participant			Х	
Chart review ^b				X

- a. Subjects will undergo either ⁶⁸Ga-RM2 PET/MRI followed within 2 weeks by ⁶⁸Ga-PMSA11 PET/MRI, or 68Ga-PMSA11 PET/MRI followed within 2 weeks by 68Ga-RM2 PET/MRI
- Subjects will be followed by chart review for 12 months from initial scan date. If a subject transfers clinical care from Stanford Healthcare, investigators may request records from the treating physician

8. ADVERSE EVENTS AND REPORTING PROCEDURES

8.1 Potential Adverse Events

The administration of the radioactive substance will feel like a slight pinprick when given by IV injection. Patients who are claustrophobic may feel some anxiety while positioned in the scanner. Also, some patients find it uncomfortable to hold one position for more than a few minutes. The subjects will not feel anything related to the radioactivity of the substance in their body. Because the radioactivity is very short-lived, the radiation exposure is low. The substance amount is so small that it does not affect the normal processes of the body.

This research study involves exposure to radiation from one ⁶⁸Ga-PSMA-11 PET/MRI. There is no radiation exposure from MRI. The effective dose from one typical maximum of 259 mBq (range: 3 to 7 mCi) administration of ⁶⁸Ga-PSMA-11 is 6.68 mSv. Therefore, the effective dose from one ⁶⁸Ga-PSMA-11 PET/MRI is 6.68 mSv, approximately equal to 13% of the limit that radiation workers (eg, a hospital X-ray technician) are allowed to receive in 1 year.

IRB-48151 Page 16 of 22 CONFIDENTIAL Protocol version 2; 15 November 2021

This research study also involves exposure to radiation from one ⁶⁸Ga-RM2 PET/MRI. There is no radiation exposure from MRI. The amount of radiation from one administration of 140 mBq of ⁶⁸Ga-RM2 is 4.76 mSv. Therefore, the effective dose from one ⁶⁸Ga-RM2 PET/MRI is 4.76 mSv, approximately equal to 10% of the limit that radiation workers (eg, hospital x-ray technician) are allowed to receive in one year.

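### Section 8.1 states the ⁶⁸Ga-RM2 dose as 4.76 mSv without the hourly-voiding condition that section 4.1.1 attaches to it, and the 7.7 mSv in section 4.1.1 does not follow from its own coefficient

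*Protocol*

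**What the plan says.** Section 4.1.1 of the protocol sets the ⁶⁸Ga-RM2 activity at 140 MBq ± 20% (printed as mBq and read here as MBq). It gives the coefficient: "The mean effective dose (14) was 0.051 mSv/MBq". It then concludes that "the effective dose from a 140-MBq injected radioactivity is 7.7 mSv", "which could be reduced to roughly 4.76 mSv with frequent bladder voiding (1-hr voids").

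Section 8.1, the description of risks, states: "The amount of radiation from one administration of 140 mBq of ⁶⁸Ga-RM2 is 4.76 mSv". It carries that number to the scan: "Therefore, the effective dose from one ⁶⁸Ga-RM2 PET/MRI is 4.76 mSv, approximately equal to 10% of the limit that radiation workers" may receive in a year. Voiding is not mentioned there.

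The procedures in section 2.4 contain two relevant instructions: "Participant will be asked to drink 1 to 2 glasses of water before arrival at the clinic" and "Participant will void immediately prior to the scan". The RM2 scan starts about 45 minutes after injection. Sections 5.2 and 6.2 add no voiding instruction.

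For the other tracer, section 4.1.2 takes the cautious route: "We used the maximum potential administered activity of 7 mCi and the higher of the reported dosimetry values". This gives 6.68 mSv, which section 8.1 repeats as 13% of the worker limit.

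**The concern.** At the same 140 MBq, two sections give two different doses. The risk section uses the lower one and leaves out what it depends on. A reader of section 8.1 alone cannot tell that 4.76 mSv assumes hourly voiding, or that the study procedures do not ask for it. The number one would use as a check, 7.7 mSv in section 4.1.1, does not agree with the coefficient printed just before it.

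What is at stake is the accuracy of the exposure statement for an investigational tracer that every participant receives. The omission also changes how the two tracers compare. Section 8.1 shows RM2 (4.76 mSv) below PSMA-11 (6.68 mSv), whereas section 4.1.1's figures without hourly voiding put RM2 above it, even though PSMA-11 is stated at its maximum activity and RM2 at its nominal one.

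**Working it through.** **Inputs**

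- RM2 activity: 140 MBq ± 20%, so at most 140 × 1.2 = 168 MBq (sections 2.4 and 4.1.1).
- RM2 coefficient: 0.051 mSv/MBq (section 4.1.1, stated twice).
- RM2 dose at 140 MBq: 7.7 mSv, or roughly 4.76 mSv with 1-hour voids (section 4.1.1); 4.76 mSv with no condition, 10% of the limit (section 8.1).
- PSMA-11: 259 MBq, 0.0258 mSv/MBq, 6.68 mSv (section 4.1.2), 13% of the limit (section 8.1).
- The annual worker limit is not stated. It is taken as 50 mSv, an assumption that fits both printed percentages: 6.68 / 0.13 = 51.4 and 4.76 / 0.10 = 47.6.

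The formula throughout is effective dose = activity × coefficient.

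**1. The PSMA-11 figure reproduces.** 259 × 0.0258 = 6.68 mSv.

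**2. The RM2 figure in section 4.1.1 does not.** 140 × 0.051 = 7.14 mSv. If the coefficient was rounded, it lies between 0.0505 and 0.0515, which gives only 7.07 to 7.21 mSv. The printed 7.7 mSv needs either 7.7 / 140 = 0.055 mSv/MBq or 7.7 / 0.051 = 151 MBq. The gap is 7.7 − 7.14 = 0.56 mSv, or 0.56 / 7.14 = 7.8%.

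**3. The section 8.1 figure is the hourly-voiding figure.** 4.76 / 140 = 0.034 mSv/MBq. The protocol never states this coefficient, but 4.76 is the number that section 4.1.1 ties to 1-hour voids. Compared with the doses without that condition:

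- against 7.7 mSv: 2.94 mSv lower, 1 − 4.76 / 7.7 = 38%
- against 7.14 mSv: 2.38 mSv lower, 1 − 4.76 / 7.14 = 33%

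**4. Dose and share of the assumed 50 mSv limit, at nominal and maximum permitted activity**

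| Basis | mSv/MBq | 140 MBq | 168 MBq |
|---|---|---|---|
| Stated coefficient | 0.051 | 7.14 mSv (14.3%) | 8.57 mSv (17.1%) |
| Implied by 7.7 mSv | 0.055 | 7.70 mSv (15.4%) | 9.24 mSv (18.5%) |
| 1-hour voids, implied by 4.76 mSv | 0.034 | 4.76 mSv (9.5%) | 5.71 mSv (11.4%) |

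**5. Both scans together, RM2 at 140 MBq.** On section 8.1's figures, 6.68 + 4.76 = 11.44 mSv. With section 4.1.1's RM2 dose without hourly voiding, 6.68 + 7.14 = 13.82 mSv to 6.68 + 7.7 = 14.38 mSv.

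**The case against.** The 4.76 mSv figure is not invented. Section 4.1.1 gives it with its condition, so the protocol as a whole discloses both values. Participants drink water beforehand and void before a scan starting about 45 minutes after injection, so a first void falls within the first hour. That moves the true dose some way towards the reduced case, and the 33% to 38% shortfall should not be read as the measured error. This stands: the protocol gives no dose for a single pre-scan void, so the figures are bounds. It does not rescue section 8.1, because section 4.1.1 attaches the lower value to frequent voiding and the procedures require no further voids.

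The 168 MBq figures can also be challenged. RM2 has a nominal activity with a tolerance, whereas PSMA-11 has a prescribed range, and two of the three coefficients used at 168 MBq are back-calculated. They are proportional scalings of doses printed in the protocol, not sourced dosimetry. They remain useful for putting the two tracers on the same maximum-activity basis.

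Finally, the 7.7 mSv slip errs on the cautious side and is not carried into section 8.1. Every candidate dose at 140 MBq is modest, about 10% to 15% of the assumed limit. The consent form is not available here and may contain voiding advice or a different figure. All of this limits the consequence, but it does not resolve either inconsistency.

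**Conclusion.** Both parts of the concern hold. Section 8.1 states as the RM2 dose a value that section 4.1.1 makes conditional on hourly voiding, and the study procedures do not secure that condition. Relative to the dose without it, the stated figure is 2.38 to 2.94 mSv (33% to 38%) low, and the share of the worker limit would be about 14% to 15% instead of 10%. Separately, 7.7 mSv exceeds what 0.051 mSv/MBq gives at 140 MBq by 0.56 mSv, and rounding does not account for it.

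The percentages of the limit rest on the assumed 50 mSv. Which of 7.14 and 7.7 mSv is right cannot be settled without the dosimetry publication. This is an error in the description of risk; it has no bearing on the endpoint, the sample size or the analysis. It should be corrected.

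**What to change.** 1. Check the dosimetry source and reconcile section 4.1.1. Either replace 7.7 mSv with 7.14 mSv, or state the coefficient or activity from which 7.7 mSv was derived.
2. Restate section 8.1 with the reconciled dose that does not depend on hourly voiding: 7.14 to 7.7 mSv at 140 MBq, about 14% to 15% of the limit. State the limit used.
3. Because section 8.1 gives PSMA-11 at its maximum activity, also give RM2 at 168 MBq: 8.57 to 9.24 mSv, to be narrowed to one value by step 1.
4. Mention 4.76 mSv (140 MBq) or 5.71 mSv (168 MBq) only with the 1-hour-void condition beside it. If the lower figure is to be relied on, add an instruction in section 2.4 to void hourly after the RM2 injection.

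The cost is one source check and a wording amendment to sections 4.1.1 and 8.1. The stated RM2 exposure becomes less favourable. Participants receive one extra instruction if the lower figure is kept. If the consent form carries the same number, it needs the same edit. No administered activity changes.
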